2. LIST OF ABBREVIATIONS

ADR	Adverse Drug Reaction
AE	Adverse Event
CI	Confidence Interval
CRF	Case Report Form
CTMF	Clinical Trial Master File
CTP	Clinical Trial Protocol
CTR	Clinical Trial Report
eCRF	Electronic Case Report Form
EDC	Electronic Data Capture
EudraCT	European Clinical Trials Database
EU-QPPV	European Union – Qualified Person for Pharmacovigilance
FAS	Full Analysis Set
FEV ₁	Forced Expiratory Volume in one second
GCP	Good Clinical Practice
GPSP	Good Post- marketing Study Practice
FVC	Forced Vital Capacity
IEC	Independent Ethics Committee
IRB	Institutional Review Board
ISF	Investigator Site File
J-PAL	Japanese Pharmaceutical Affairs Law
J-RMP	Japan Risk Management Plan
MedDRA	Medical Dictionary for Regulatory Activities
MR	Medical Representative
NBI	Nippon Boehringer Ingelheim Co. Ltd.
OPU	Operative Unit
PEFR	Peak Expiratory Flow Rate
PMDA	Pharmaceuticals and Medical Devices Agency
PMS	Post Marketing Surveillance
SAE	Serious Adverse Event
SPC	Summary of Product Characteristics
TCM	Trial Clinical Monitor
TDMAP	Trial Data Management and Analysis Plan
TMM	Team Member Medicine
TMW	Trial Medical Writer
TSAP	Trial Statistical Analysis Plan

4. ABSTRACT

Name of company: Boehringer Ingelheim			
Name of finished medicinal product: SPIRIVA Respimat			
Name of active ingredient: Tiotropium bromide			
Protocol date: 15 April 2015	Study number: 205.525	Version/Revision: Ver 1.0	Version/Revision date: n.a.
Title of study:	Specific Use-Result Surveillance of Spiriva Respimat in asthmatics (patients with severe persistent asthma)		
Rationale and background:	The safety of Spiriva® 2.5 µg Respimat® 60 puffs (hereinafter referred to as Spiriva® Respimat®) in patients with severe persistent asthma under the real-world use was not confirmed in clinical trials.		
Research question and objectives:	This PMS is designed; To investigate the safety and effectiveness of Spiriva Respimat in patients with severe persistent asthma under real-world use.		
Study design:	Non-interventional, observational study based on new data collection		
Population:	Inclusion criteria: 
• Patients diagnosed with severe persistent bronchial asthma• Patient aged ≥ 15 years old• Patients who are naive to Spiriva respimat and receive Spiriva Respimat for the first time for the treatment of bronchial asthma on top of at least ICS treatment.		
Variables:	Demographics Medical history/baseline conditions Previous/concomitant therapies Pulmonary function test (peak expiratory flow rate, forced expiratory volume in 1 second, forced vital capacity), if available Asthma severity and asthma control status, if available ACQ 6 score, if available Spiriva Respimat administration Adverse event Safety laboratory test (if corresponding AEs are reported)		
Data sources:	Patients data will be gathered by electronic Case Report Form on EDC		
Study size:	300 (safety set)		
Data analysis:	Descriptive		
Milestones:	Final report will be made by 1 Apr 2018 Study result in re-examination will be submitted to PMDA (Jan. 2019)		

5. AMENDMENTS AND UPDATES

There are currently no amendments to the protocol.

6. MILESTONES

Milestone	Planned Date
Start of data collection	1 Jun 2015
End of data collection	31 Aug 2017
Study progress report	None
<Registration in the EU PAS register>	To be registered
Final report of study results:	1 Apr 2018 (Study result in re-examination will be submitted to PMDA by Jan. 2019)

7. RATIONALE AND BACKGROUND

Tiotropium is one of the most widely used long-acting bronchodilators worldwide for the treatment of COPD, and now, after systematic clinical investigation, it is proposed to be designated for relief of various symptoms associated with the obstructive impairment of airways due to the following diseases: chronic obstructive pulmonary disease (chronic bronchitis, emphysema), bronchial asthma.

Tiotropium delivered via the RESPIMAT inhaler once daily demonstrated consistent and significantly improved lung function parameters in the Phase III trials despite the fact that the requirement for stable asthma maintenance therapy at baseline and throughout the treatment period might impose limitations on the effect size that can be achieved with an additional treatment. In addition to the improvements in lung function, patients who remained symptomatic despite treatment with at least a high-dose ICS+LABA or medium-dose ICS were shown to have a symptomatic benefit from taking tiotropium [\[U13-1598-01\]](#).

Tiotropium delivered via the RESPIMAT inhaler once daily also demonstrated acceptable long-term safety and tolerability when administered at a dose of 5 µg (Tio R5) to adult patients with asthma. Exposure to tiotropium in the clinical program covered more than 1000 patient-years in more than 2200 patients. The overall frequencies of AEs, drug-related AEs, and SAEs were similar across all treatment groups in trials with the same duration and patient population. In general, no specific concerns with regard to abnormal vital signs were raised for patients who took tiotropium. There were no consistent patterns of increases in particular AEs for the tiotropium treatment groups compared to the placebo in any subgroup analysis. No deaths were reported during the entire clinical program [\[U13-1598-01\]](#).

According to the current guidelines for the treatment of asthma, although various treatment options are available for long-term asthma management including ICS as the first-line therapy and other additional therapies depending on asthma severity (e.g., LABA, leukotriene receptor antagonist, theophyllines, antihistamines, oral steroids, anti-IgE), improvement of symptoms is insufficient in many patients (i.e., uncontrolled and/or at potential risk of asthma exacerbation), and there is a growing medical need for additional therapeutic options for the treatment of asthma [\[! "#\\$%"&%\]](#) Responding to the medical needs, inhaled administration of anticholinergic bronchodilator Tio R5 as a new additional maintenance therapy in patients with asthma who remain symptomatic despite treatment with at least ICS has significance in managing lung function and symptoms of asthma patients more appropriately and may be an important paradigm shift in the treatment of asthma patients.

Result of PMDA review

PMDA judged that the 5-µg dosage form was suitable only for patients with severe persistent asthma and the 2.5-µg dosage form was suitable for patients with mild to moderate persistent asthma. But the 2.5-µg dosage form is not established for marketing and the 5-µg dosage form has no data to ensure the dose of 2.5 µg in one inhalation because Respimat inhaler can only maintain quality assurance with two inhalations at a time.

For the above reason including PMDA review, Spiriva Respimat (5-µg dosage form) for use in severe persistent asthmatics age 15 or over was approved on November 18 2014 in Japan.

PMDA instructed NBI to conduct the PMS with sever persistent asthmatics at age 15 or over as an approval condition in J-RMP.

Japanese regulation related to Post Marketing Surveillance (PMS)

This PMS study is planned according to the Japanese Law for Ensuring the Quality, Efficacy, and Safety of Drugs and Medical. The law requires in principle that data on the safety and effectiveness of all launched products to be accumulated under real-world clinical practice. The data collected in the PMS study are required to be submitted to the Pharmaceuticals and Medical Devices Agency (PMDA), the local regulatory agency in Japan, according to the process of re-examination which will take place 4 years after approval of registration. The PMS study is a part of the local Risk Management Plan in Japan (J-RMP) to be submitted to PMDA at New Drug Application.

8. RESEARCH QUESTION AND OBJECTIVES

As the submission data package for registration in Japan, we participated in two studies in adult patients with severe persistent asthma (Studies 205.416 and 205.417) and two studies (Studies 205.418 and 205.419) in adult patients with moderate persistent asthma, and we comparatively investigated the dose response between Japanese and non-Japanese by using two doses (Tio R2.5 and Tio R5). With the addition of the domestic long-term administration study in Japanese patients (Study 205.464), we investigated the validity of selecting a dose of 5 µg in Japanese asthma patients [[U13-1598-01](#)].

In the clinical trials, 212 Japanese patients with asthma received Tio R5 up to 52 weeks and some concomitant asthma therapies were allowed. However the clinical trials reflected a limited controlled experiment that might not generalize to the population, setting or condition and might not be reflected due to prohibited concomitant drugs or exclusion criteria of complicating diseases. The primary aim of clinical trials is to measure the key clinical efficacy as an end point in a limited population and clinical setting. PMS is likely to improve data monitoring and can collect post-marketing safety data in response to specific safety concerns. Even though there was no safety concern reported in patients with asthma based on the results of clinical trials, PMDA directed NBI to conduct PMS to fulfill regulatory obligations established as a condition of marketing approval.

The objective of this PMS is to investigate the safety and effectiveness of Spiriva Respimat in patients with severe persistent asthma under real-world use.

9. RESEARCH METHODS

9.1 STUDY DESIGN

This is a non-interventional study based on newly collected data under routine medical practice.

This PMS is designed to investigate the safety and effectiveness of Spiriva Respimat in patients with severe persistent asthma on top of at least ICS maintenance treatment under real-world use.

[figure not shown]
9.1.1 Outcomes: effectiveness

9.1.1.1 Primary outcome

There is no primary outcome for effectiveness as the primary objective of a PMS is evaluating safety. The primary outcome for safety is described in Section [9.1.2.1](#).

9.1.1.2 Secondary outcome

- Change from baseline in asthma control status at Week 52

9.1.1.4 Assessment of effectiveness

Asthma control status:

Asthma control status will be assessed based on the “Asthma prevention and management guideline” [[! "#\\$%"&%](#)

9.1.1.4: 1 Asthma control status Table

Patients control status	Well-controlled	Insufficiently-controlled	Poorly-controlled
	Meet all the criteria	Meet 1 or 2 criteria	Meet all of 3 Criteria
Asthma symptoms (in the daytime or at night)	None	Once or more a week	Once or more a week
Use of reliever	None	Once or more a week	Once or more a week
Limitation of activities, including exercise	None	Restricted	Restricted

9.1.2 Outcomes for safety

9.1.2.1 Primary Outcome

The primary Outcome is the absolute and relative (%) frequency of patients with suspected adverse drug reactions (ADRs).

Safety will be assessed by use of the following other parameters of interest:

- Adverse events irrespective of seriousness
- Laboratory tests (if corresponding AEs are reported)

9.2 SETTING

9.2.1 Site selection:

NBI will nominate the candidate sites which satisfied the following criteria and NBI ask the nominated sites to participate in the study.

1. Spiriva Respimat has been delivered to the site.
2. The observation of peak expiratory flow meter is done as part of the usual medical practice.

Planned number of sites: Approximately 25 Sites

A medical representative will explain the objectives, subjects and methods of the surveillance to the investigator at the site and exchange a written contract with the head of the site (e.g., hospital director).

9.2.2 Selection of population

9.2.2.1 Inclusion/Exclusion criteria:

Inclusion criteria:

- Patients diagnosed with severe persistent bronchial asthmaPatient aged ≥ 15 years
- Patients who are naive to Spiriva Respimat and receive Spiriva Respimat for the first time for treatment of bronchial asthma on top of at least ICS treatment.

*:Asthma severity is defined by “Table 6 Classification of asthma severity based on the present treatment (adult)” of “Japanese Guideline for Adult Asthma 2014”[P14-15105]. Most severe persistent asthma is included in “Severe persistent asthma” indication in J-PI of Spiriva Respimat.

Exclusion criteria:

- Patients who have a contraindication to Spiriva Respimat defined in the package insert for Spiriva Respimat
- Patients who have been enrolled this study before.

9.2.2.2 Patient registration method

The registration method will be a continuous investigation system. Patients who begin treatment with Spiriva Respimat after the conclusion of the contract will be registered by entering necessary information in the EDC within 14 days whenever possible from the day of treatment initiation (inclusive).

The necessary variable for registration is gender, date of birth, start date of administration and the reason for use. And ICS treatment as of inclusion criteria will be checked in the EDC system.

Patient registration will be stopped when the target number of the study is reached. After the end of the registration period, investigators will use a signed form to confirm that patients will be registration continuously at the site. A log of all patients included into the study will be maintained at the site.

9.2.2.3 Registration period

From June 2015 to May 2016

9.2.3 Observations

After start of the treatment with Spiriva Respimat, each patient will be observed for 52 weeks (approximately 12 months) or at premature discontinuation from the PMS. Observations are made at the following time points: before first administration of Spiriva Respimat (this visit is defined as baseline), 4 weeks, 12 weeks and 52 weeks after the start of treatment, or at discontinuation.

9.2.5 Discontinuation of the study by the sponsor

NBI reserves the right to discontinue the PMS overall or at a particular PMS study site at any time for the following reasons:

1. Failure to meet expected registration overall goals or goals at a particular study site,
2. Emergence of any effectiveness/safety information that could significantly affect continuation of the PMS,
3. Violation of Good Post-marketing Study Practice (GPSP) or the contract of a study site or investigator, thereby disturbing the appropriate conduct of the PMS.

The investigator / the PMS site will be reimbursed for reasonable expenses incurred as a result of PMS termination (except in case of the third reason).

9.4 DATA SOURCES

Case Report Forms (CRFs) for individual patients will be provided by the sponsor via the Electronic Data Capture (EDC) system.

Three case books will be used. The first book is for registry (Book 1), the second book is for baseline, 4 and 12 weeks (Book 2) and the third book is for 52 weeks (Book 3).

Data are to be transmitted immediately after being entered into the eCRF at 12 weeks and 52 weeks after the start of treatment or at discontinuation. In the case that any adverse events occur, the data should be immediately entered into eCRF and transmitted.

9.5 STUDY SIZE

It is planned to enroll 360 patients with severe persistent asthma: 360 patients will initiate the Spiriva Respimat treatment, assuming 60 patients out of 360 patients will be dropped out without any data being collected.

The planned number of patients is not driven by a formal sample size calculation but is primarily based on the availability of patients eligible for Spiriva Respimat treatment.

300 patients will be registered for this study. The frequently observed ADR ($\geq 1.0\%$) in special use surveillance for Spiriva Respimat in patients with COPD was Coughing (1.2%). The frequently observed ADRs ($\geq 1.0\%$) in the clinical trial in Japanese patients with asthma were asthma (1.8%), dysphonia (1.8%) and dry mouth (1.8%). In the number of cases to be surveyed, it is evaluated if there is no possibility that the trend of incidence of these main adverse events would be largely increased compared to that of COPD patients.

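### Protocol 9.5 needs 360 registered patients to give a safety set of 300 but says 300 will be registered, and the registration stop in 9.2.2.2 has no number; a lesser point is that 9.5 does not state what precision 300 patients give

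*Protocol*

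**What the plan says.** **Study size.** Protocol 9.5 opens by planning for 360 enrolled patients, all of whom start treatment. Its allowance for losses reads "assuming 60 patients out of 360 patients will be dropped out without any data being collected". It says that the number rests on patient availability and not on a formal calculation. It then states "300 patients will be registered for this study". The abstract gives the study size as 300 and labels that figure the safety set.

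**Registration stop.** Protocol 9.2.2.2 says "Patient registration will be stopped when the target number of the study is reached" and gives no figure. Patients are registered after treatment starts, within 14 days where possible. Registration itself captures gender, date of birth, start date and reason for use.

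**Losses after registration.** Protocol 9.7 makes a patient ineligible for all analyses if no safety observation is recorded after registration. SAP Table 6.2:1 excludes from the safety set patients with no visit (D1), no CRF (D2) or no safety observation (D3) after registration.

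**What the number is for.** Protocol 9.5 cites coughing at 1.2% as the frequent ADR (1.0% or more) in the COPD surveillance. For the Japanese asthma trials it cites asthma, dysphonia and dry mouth at 1.8% each. It adds that "it is evaluated if there is no possibility that the trend of incidence of these main adverse events would be largely increased" relative to COPD patients. The primary outcome in 9.1.2.1 is the number and percentage of patients with suspected ADRs. SAP 7.8.1 plans ADR frequencies by preferred term and 95% CIs for subgroup odds ratios. The available text plans no interval for the overall ADR frequency or for single ADRs.

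**The concern.** The figure 300 is used for two different quantities: patients in the safety set (abstract) and patients registered (9.5). These can be equal only if nobody is lost between registration and analysis, yet 9.7 and SAP D1 to D3 exist to handle exactly those losses. Because 9.2.2.2 gives no figure, a reader has to go to 9.5 for the stopping number and finds both 360 and 300 there. At stake is whether registration closes 60 patients early and the safety set falls short of its stated size.

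The second, smaller matter is how 9.5 describes what the number can deliver. It frames the aim in absolute terms, without a threshold for a large increase and without a statement of precision.

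**Working it through.** **1. Reproduce the plan's figure.** Inputs from 9.5: 360 enrolled, 60 without data.

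- Evaluable: 360 − 60 = 300, which matches the abstract.
- Loss rate: 60/360 = 1/6 = 16.7%.
- Check in reverse: 300 / (1 − 1/6) = 360.

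The arithmetic is sound. The conflict lies in the word attached to 300 in 9.5.

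**2. Possible readings of the stop.**

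| Reading | Registered | Safety set |
|---|---|---|
| Stop at 360, the 60 lost after registration | 360 | 360 − 60 = 300 |
| Stop at 300, same loss rate after registration | 300 | 300 × 5/6 = 250 |
| The 60 start treatment but are never registered; stop at 300 | 300 | 300 less the 9.7 exclusions (size not given) |

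Only the first gives the abstract's 300 and still leaves room for the exclusions after registration.

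**3. Cost of the shortfall.** Chance of at least one case of an ADR with true rate 1.2%, from 1 − (1 − 0.012)^n:

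- n = 300: 1 − 0.988^300 = 97.3%
- n = 250: 1 − 0.988^250 = 95.1%

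**4. Precision for single ADRs.** Exact (Clopper-Pearson) 95% limits. At 1.2%, 300 × 0.012 = 3.6 patients with cough are expected. At 1.8%, 300 × 0.018 = 5.4 patients are expected.

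| Observed | Rate | 95% CI |
|---|---|---|
| 3/300 | 1.0% | 0.2 to 2.9% |
| 4/300 | 1.3% | 0.4 to 3.4% |
| 5/300 | 1.7% | 0.5 to 3.8% |
| 3/250 | 1.2% | 0.2 to 3.5% |

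The upper limit for 4/300 is 3.38/1.2 = 2.8 times the COPD cough rate.

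**5. What n = 300 can exclude.** Assumptions: the true cough rate is 1.2%, and 1.2% is a fixed reference (9.5 gives no denominator for it). The fold increases are illustrative, since 9.5 sets no threshold. The probability is that the two-sided 95% upper limit falls below the multiple.

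| Multiple of 1.2% | Needs | Probability |
|---|---|---|
| 2 (2.4%) | X ≤ 2 | 30% |
| 3 (3.6%) | X ≤ 4 | 71% |
| 4 (4.8%) | X ≤ 7 | 97% |

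If the true rate were 0.8% (an assumption), the same cut-offs give 57%, 90% and 99.7%. With a one-sided 95% limit and a true rate of 1.2%, a tripling is excluded when X ≤ 5, with probability 85%.

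**The case against.** **On the registration number.** The best defence is that nothing conflicts. Registration follows the start of treatment and itself records data, so patients lost with no data at all may never have been registered, which leaves 300 registered. The documents allow this reading. It sits poorly with the statement that all 360 are enrolled, since no enrolment step other than registration is described. It also makes no allowance for the exclusions after registration, so the safety set would still end somewhat below 300.

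It is also fair to say that the word was probably a slip for the safety set, that the number has no formal basis, and that the effect is small. Registration was planned to close in May 2016 and the SAP is dated 1 October 2017, so on the planned dates the stop was past when the SAP was finalised. These points limit the importance but leave the two meanings of 300 unreconciled.

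A reader might infer that the study is planned to yield only 250 evaluable patients. The documents do not support that: 250 needs both a stop at 300 and the full loss afterwards.

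**On the COPD aim.** A reader might infer that 9.5 promises a proof that 300 patients cannot supply, or that 300 is too few to be useful. Neither holds. The sentence is an awkwardly worded aim in a study that 9.7 calls descriptive, and no finite sample could meet it literally. It concerns large increases, and a fourfold rise would very probably be excluded. Doubling is an illustrative threshold that the plan does not set. Nor is there a complete lack of COPD information for the other three ADRs: listing only cough at 1.0% or more implies that they were below 1.0% in COPD, although the rates are not given. Readers could derive intervals from the planned counts, and SAP 7.8.1 defers some adverse event detail to references that are not available here. What remains is a cheap improvement in reporting.

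**Conclusion.** The main point holds as an inconsistency in a number that governs when registration stops. Protocol 9.5 supports 360 registered and 300 analysed, yet states 300 registered, and 9.2.2.2 does not settle it. If registration stopped at 300, the safety set would be below the stated 300: about 250 if the 60/360 loss falls entirely after registration, and an unstated smaller shortfall if the 60 are never registered. The loss of information is modest (97.3% to 95.1% for seeing a 1.2% ADR at least once). It should be corrected, but it does not threaten the study.

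The point about precision is secondary and minor. With cough at its COPD rate, 300 patients are informative about large increases but not about a doubling, and the plan should say so. That rests on treating 1.2% as both the true rate and a fixed reference.

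**What to change.** - **Protocol 9.5, 9.2.2.2 and abstract:** use one set of numbers, with registration stopping at 360 to obtain about 300 in the safety set. If the sponsor meant the 60 as patients who start treatment but are never registered, say so, give 300 as the stop, and restate the safety set as somewhat below 300 after the 9.7 exclusions.
- **Protocol 9.5, COPD sentence:** replace the absolute aim with the precision available at n = 300, for example 4/300 with its exact interval and the statement that a doubling would usually not be excluded.
- **SAP 7.8.1:** add descriptive exact 95% CIs for the primary ADR frequency and the four named ADRs. For the four named ADRs, show the reference rates from 9.5 labelled by source: cough 1.2% (COPD surveillance); asthma, dysphonia and dry mouth 1.8% (asthma trials), noting that COPD rates for these three are not given but are implied to be below 1.0%.

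The cost is a few sentences, one table column and a less favourable statement of what the study can show. No formal test and no patients beyond the planned 360 are needed, and the study stays descriptive.
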